Using a randomized experimental design, 300 parents of 2-5 year old children (predominantly African American and economically disadvantaged) referred for behavior problems to the Family Center at Kennedy-Krieger Institute will be randomized to Parent-Child Interaction Therapy (PCIT; n=150) or Chicago Parent Program (CPP; n=150). Data on child behavior problems, parent discipline strategies, parenting self-efficacy, observed parent behavior, parent stress, and depression will be obtained from all participants at baseline and post-intervention assessments. Social risk will be assessed at intake. Parent satisfaction, attendance, and engagement in the intervention will be obtained at post-intervention. Clinical costs related to PT and non-PT treatment will be measured monthly. This innovative study will be the first to compare the effectiveness, cost, and social validity of a brief treatment designed with and for ethnic minority parents of young children against a well-established treatment considered to be the "gold standard." Determining whether a PT treatment can yield comparable effects for low-income, racial/ethnic minority parents of young children but at less cost, in less time, and with greater social validity is of significant public health importance.

2. Objectives: To compare the:

1. Effectiveness of PCIT and CPP for reducing behavior problems in a predominantly African American sample of children 2-5 years old from low-income communities. It is hypothesized that CPP will be equally as effective as PCIT for reducing child behavior problems based on parent report and observation.
2. Effectiveness of PCIT and CPP for improving parenting behavior and self-efficacy among a predominantly African American sample of parents of 2-5 year old children from low-income communities. It is hypothesized that CPP will be equally as effective as PCIT for improving parent discipline, self-efficacy, and observed parenting behavior.
3. Perceived social validity of PCIT and CPP based on parent satisfaction scores, treatment attendance, and parent engagement ratings (i.e., active parent participation in the intervention

Date: January 30, 2012
Principal Investigator: [name]
Application Number: NA_00039328

sessions). It is hypothesized that parents in the CPP condition will (a) attend a higher percent of PT sessions, (b) be more engaged, and (c) report higher satisfaction than parents in PCIT.

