Like other evidence-based PT programs, PCIT has led to substantial improvements in parent and child outcomes. However, among children with very high rates of behavior problems, researchers have reported the strongest effects with PCIT, with effect sizes ranging from .61 (parent reported child behavior problems) to 5.67 (observed parent behavior) when compared to untreated waiting-list controls. Studies have also shown that most children retain improvements 3 to 6 years post-treatment. Based on the strength of these data, PCIT is considered to be the "gold standard" among individually-delivered PT. It is also one of the most widely disseminated PT programs in the United States, with "PCIT laboratories" for training graduate students and clinicians offered at 8 major universities.

Date: January 30, 2012
Principal Investigator: [name]
Application Number: NA_00039328

Although impressive, these data only reflect outcomes for “completers,” parents who start PCIT and do not drop out before they have completed the program. In a recent study of attrition from PCIT, 36% of parents prematurely stopped attending PCIT and the most common reason cited by parents was “disagreement with the treatment approach.” In addition, like many other PT programs, the strongest predictor of premature termination was low socioeconomic status. These data suggest that PCIT may not be viewed as useful or relevant by many economically disadvantaged parents. In addition, since most PCIT studies include samples that are predominantly non-Latino White, it is unclear how effective this program is among low-income ethnic minority families. Although there have been some efforts to adapt PCIT to other populations, rigorous trials of these adaptations have not been conducted. In sum, like many treatments identified as “gold standards,” its validity for low income, ethnic minority populations has not been sufficiently evaluated.

The Chicago Parent Program: Description, Critique, and Justification. Funded by a grant from the NINR, the Chicago Parent Program (CPP) was developed in 2002 specifically to address the gap in evidence-based PT programs for ethnic minority parents. Created in collaboration with an advisory group of African American and Latino parents, the CPP was designed to improve parenting and reduce child behavior problems using strategies that are culturally and contextually relevant for ethnic minority parents of young children living in low-income urban neighborhoods.

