Exclusion criteria are parent(s) who (a) has (have) severe mental illness that would interfere with their ability to participate in PT (measured by the Psychosis Subscale of the Basic-24 or diagnostic intake clinician assessment) and/or (b) is (are) actively using drugs or alcohol, based on clinician assessment at intake. Foster parents or relatives without legal status for the child are excluded since they may not be able to complete the study.. Children who are actively suicidal, psychotic, or who have significant developmental delay (i.e., fail developmental screening using Ages and Stages Questionnaire at intake), congenital, genetic, or sensory abnormalities that interfere with the child’s understanding, cooperation, and/or participation in PCIT or CPP will be excluded and referred for appropriate treatment services or hospitalization. Children diagnosed with autism or Pervasive Developmental Disorder will also be excluded since there is no evidence that CPP or PCIT is effective with these populations.

6. Drugs/ Substances/ Devices

- a. NA
- b. NA.
- c. NA

7. Study Statistics

- a. Primary outcome variables: Child behavior problems (parent report and observed from video recorded parent-child play/clean-up), parenting self-efficacy, parent discipline, parent behavior (observed from video recorded play/clean-up), parent satisfaction, parent engagement in the intervention, parent attendance in PT sessions.
- b. Secondary outcome variables: cost variables are those related to (1) time required to administer PT (including lost time for missed appointments) and additional non-PT therapy services used by parent or child (i.e., individual therapy, medications); (2) therapist time, (3) parent time, (4) childcare provided during CPP sessions; (5) space (including one-way mirror).
- c. Sample Size and Statistical Plan: Sample size in this equivalence study is designed to determine whether CPP is as effective as PCIT for the targeted clinical population (i.e., outcomes do not differ clinically or statistically). We used CBCL scores (child behavior problems) to estimate the sample size positing the null hypothesis that the absolute difference in the post intervention means between the CPP and PCIT groups will be > 0.5 standard deviations (i.e., > 5 point difference on the CBCL). The alternative hypothesis is that the absolute difference in the two means is less than or equal to 0.5

Date: January 30, 2012
Principal Investigator: [name]

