Application Number: NA_00039328

standard deviations. We will use the more conservative two-sided test. Thus, with 300 participants (150/condition) we will have 99% power to detect this difference using a two-sample comparison of means with alpha=0.05.

Hypothesis testing will mainly be conducted using repeated-measures MANOVA. Should the MANOVA be significant, univariate ANOVA will follow to identify the source of those differences. MANOVA was determined to be a more desirable approach than random regression models because MANOVA corrects for multiple tests of hypotheses. All baseline difference analyses and hypothesis testing will be conducted using 2-tailed tests and alpha =.05 (except tests to examine baseline differences between conditions, which will use .01 to correct for the multiple tests of hypotheses).

d. Early stoppage rules. Interventions will be discontinued if (a) more than 50% of parent participants in either condition report dissatisfaction on consumer satisfaction surveys with their assigned intervention or (b) more than 50% of child participants' CBCL scores (in either condition) worsen from baseline by $> .5$ SD. In this event, the research team will immediately convene with the members of the DSM committee to carefully review the protocol, reasons for dissatisfaction, and recommendations for change. A data safety and monitoring committee will meet early in the first year of the study to make additional recommendations for stoppage rules.

8. Risks

- a. Medical risks. Parent-Child Interaction Therapy and the Chicago Parent Program are psychosocial parent training interventions that have shown no evidence of medical risk. The major risks of this study are disclosure of confidential information and discomfort with the personal nature of some of the survey questions. These risks are no greater than what parents would be exposed to in a mental health treatment setting.
- b. Efforts to minimize risk. Efforts have been taken to minimize risk through appropriate training of research and clinical staff and the use of random number subject identifiers. All therapists have licensed and experienced therapists and have completed the appropriate training (PCIT or CPP).

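### Four primary domains hypothesised to be equal between programs have no stated equivalence margin, and the planned MANOVA gives no test that could show equivalence on them

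*Combined protocol and SAP*

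**What the plan says.** Section 2 (Objectives) states two hypotheses of equal effectiveness. Objective 1: "CPP will be equally as effective as PCIT for reducing child behavior problems based on parent report and observation". Objective 2: "CPP will be equally as effective as PCIT for improving parent discipline, self-efficacy, and observed parenting behavior". Together they cover five domains: child behaviour by parent report (CBCL), child behaviour by observation (DPICS), discipline (PQ), self-efficacy (TCQ) and observed parenting (DPICS). Section 7a lists all five as primary. The other three primary outcomes (satisfaction, engagement, attendance) carry superiority hypotheses under Objective 3 and need no equivalence margin.

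Section 7c introduces the one equivalence null in the document: "We used CBCL scores (child behavior problems) to estimate the sample size positing the null hypothesis". The limit is 0.5 SD, glossed as "i.e., > 5 point difference on the CBCL". The same section then says that hypotheses will mainly be tested by repeated-measures MANOVA, two-tailed at 0.05, and that "Should the MANOVA be significant, univariate ANOVA will follow to identify the source of those differences". It names no equivalence test, no confidence-interval rule and no margin for TCQ, PQ or either DPICS domain.

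**The concern.** A claim of equal effectiveness needs a limit on the difference that would still count as equal, and a test or interval judged against that limit. For these four domains the plan states neither. The MANOVA asks whether there is any difference, and the outcome-level ANOVAs follow only if the answer is yes. The result that the hypotheses predict, no visible difference, is the one after which no outcome-level test is specified.

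What would be left is a non-significant joint test, which does not show equivalence. CPP is put forward as the cheaper program with comparable effects (Objective 4). A report of equal benefit for parenting could therefore be made while CPP was materially worse on one parenting outcome.

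**Working it through.** **Inputs.** From section 7c: 150 per arm, two-sided alpha 0.05, limit 0.5 SD on the CBCL, stated power 99%. From Table 1: TCQ one score, PQ three subscales, DPICS parent behaviour six listed categories (counting positive and negative affect separately), so 1 + 3 + 6 = 10 scores for Objective 2. Assumed: one post-intervention comparison, no loss to follow-up, SD units.

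**1. The plan's own figure.** SE = sqrt(2/150) = 0.1155 SD, and 0.5/0.1155 = 4.330.
- As a two-sided difference test: Phi(4.330 - 1.960) = Phi(2.370) = 99.1%.
- As two one-sided equivalence tests with true difference zero: 2 x Phi(4.330 - 1.645) - 1 = 99.3% (90% CI), or 2 x Phi(2.370) - 1 = 98.2% (95% CI).

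The stated 99% reproduces. The sample-size arithmetic is sound, but it is done for the CBCL only.

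**2. Domains against margins.**

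| Domain | Equal-effectiveness hypothesis | Primary (7a) | Margin stated |
|---|---|---|---|
| Child behaviour, CBCL | Objective 1 | yes | 0.5 SD / 5 points |
| Child behaviour, DPICS | Objective 1 | yes | none |
| Discipline, PQ | Objective 2 | yes | none |
| Self-efficacy, TCQ | Objective 2 | yes | none |
| Observed parenting, DPICS | Objective 2 | yes | none |

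**3. What a non-significant result is worth.** Suppose CPP is truly worse by 0.3 SD on one outcome and equal on the rest.
- Tested alone: 0.3/0.1155 = 2.598, power = Phi(2.598 - 1.960) = Phi(0.638) = 73.8%, so non-significant 26% of the time.
- In a two-group MANOVA of p outcomes with equal correlation r, the noncentrality is (150/2) x d^2 x k, with k = [1 + (p - 2)r] / [(1 - r)(1 + (p - 1)r)], referred to F with p and 299 - p degrees of freedom.

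For p = 10 (F on 10 and 289 df, critical value 1.864) and d = 0.3, where 75 x 0.09 = 6.75:

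| r | k | Noncentrality | Non-significant |
|---|---|---|---|
| 0 | 1 | 6.75 | 65% |
| 0.3 | 3.4/2.59 = 1.313 | 8.86 | 53% |
| 0.5 | 5/2.75 = 1.818 | 12.27 | 37% |

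With 5 outcomes the figure is 52% at r = 0 and 27% at r = 0.5. For a true loss of 0.5 SD it is 1% alone, and 15%, 5.5% and 0.9% with 10 outcomes at r = 0, 0.3 and 0.5.

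**4. What margins the trial could support.** Power for a 95% CI to lie inside margin m with true difference zero is 2 x Phi(m/0.1155 - 1.960) - 1. The joint column is its fifth power: all five domains pass, same margin, one score each, independent.

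| Margin | m/0.1155 - 1.960 | Per outcome | All five |
|---|---|---|---|
| 0.5 SD | 2.370 | 98% | 91% |
| 0.4 SD | 1.504 | 87% | 49% |
| 0.3 SD | 0.638 | 48% | 2.5% |

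**The case against.** The best reply is that 0.5 SD is a standardised limit. Section 7c opens by describing the sample size in terms of the trial's outcomes generally, uses the CBCL to work it out, and gives the limit in SD units before points. On that reading the sponsor may have meant 0.5 SD throughout. This largely stands: the limit can be carried over. A reader might infer that it cannot, because section 3 quotes PCIT effects from .61 for parent report to 5.67 for observed parenting, so that 0.5 SD is a very different share of each. That does not follow. A margin that is a small share of the reference effect is strict, not unusable, and the larger figure is the top of a range against untreated waiting-list controls, in data the protocol says reflect completers only. What remains is that no sentence extends the limit or says which PQ or DPICS score it would apply to.

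The second reply is that the percentages in step 3 measure the difference test and its gate, not the missing margin. That is correct: adding margins while keeping the gate would leave them unchanged, so the fix has to do both. Zero correlation is also the worst case among those shown, hence the range. The plan does not say which scores enter which MANOVA, and the calculation ignores the repeated measures.

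Third, testing is only mainly by MANOVA, Objective 4 uses improvement from baseline as an effect size, and nowhere does the document say that non-significance will be read as equality. So it would be too strong to say that the plan yields no outcome-level estimate of any kind, or that the sponsor intends that reading. The supported statement is that no outcome-level test or decision rule for equivalence is specified.

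**Conclusion.** The concern holds as a gap in the decision rule. Four of the five primary domains with an equal-effectiveness hypothesis have no stated margin. Under the stated analysis, equivalence on them could rest only on a non-significant joint test. That follows from the text alone. The size rests on assumptions: with 150 per arm, no loss and a single comparison, a 0.3 SD loss on one outcome is missed 26% of the time when tested alone, and 37-65% of the time in an assumed 10-outcome MANOVA with equal correlation from 0.5 down to 0.

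Two further inferences are not supported. The 36% quoted in section 3 is drop-out from PCIT treatment in another study. Assessments here are timed from baseline, so it cannot be read as loss of outcome data in both arms. The margins in step 4 are what the sample size can attain at given power, not a range of clinically acceptable limits.

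The CBCL is a separate matter: there a limit exists but is not carried into the analysis. Repairing that would still leave these four domains without a criterion. The sponsor should make this change.

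**What to change.** In section 7c, before outcome data are compared between arms:

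- Name one score (or the listed subscales) and the time point for each of the four domains. The time point matters because section 4b has CPP lasting about 3 months and PCIT usually 6-8, with assessments at 4 and 9 months.
- State an equivalence margin for each. Either extend the 0.5 SD limit explicitly, converted to the instrument's units with a fixed SD such as the pooled baseline SD, or justify a narrower one.
- Report the CPP-PCIT difference with a two-sided 95% CI for each outcome, whether or not the MANOVA is significant.
- Claim equal effectiveness only for outcomes whose CI lies inside the margin, and say whether a claim for a whole objective needs every domain to pass.
- For any outcome without a margin, report the estimated difference and make no equivalence claim.

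The cost is a paragraph and a small table, with no new data or participants. The downside is that some outcomes may end as inconclusive. Extending 0.5 SD keeps power high (98% per outcome), while 0.4 or 0.3 SD lowers it to 87% or 48%. If all five domains must pass, the step 4 figures are 91%, 49% and 2.5%. Positively correlated outcomes would do somewhat better, and loss to follow-up or a true difference other than zero would do worse.

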4. Cost and consequences of PCIT versus CPP using a cost-consequence analysis as they relate to treatment effect size (improvement from baseline), clinical costs, and perceived social validity. CPP is hypothesized to yield comparable effects but at less cost and with greater satisfaction.
5. Degree to which parent stress and depressive symptoms moderate intervention effectiveness for PCIT and CPP. It is hypothesized that there will be no difference between PCIT and CPP in the moderating effects of baseline parent stress and depressive symptoms on parent or child behavior.

In addition, **one exploratory aim will be tested:** Is PCIT more effective than CPP for some families? It is possible that PCIT is more effective for families with specific risk factors. We will examine differences in PT program effects based on baseline child behavior problems (severity of behavior problems; externalizing versus internalizing problems) and degree of family social risk.

3. Background:

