b. Study duration and visits: Following consent, parents will be assigned to the appropriate block consisting of the next CPP group or the next available PCIT therapist. Participating parents and children will complete three assessment phases: baseline, 4 months post-baseline, and 9 months post-baseline. Each assessment phase includes parent-report surveys on child behavior problems, parenting self-efficacy, parent discipline strategies, stress, depressive symptoms, and attachment, and a 15- minute videotaped parent-child free play interaction (Dyadic Parent-Child Interaction Coding Systems; DPICS), followed by a clean-up session. Videotaped DPICS assessments will be coded by research colleagues at the University of Iowa ([name].) A Data Use Agreement will be obtained between Drs. [name], University of Iowa and [name], Johns Hopkins School of Nursing. Assessments typically require 45-75 minutes at each phase. All measures are described in Table 1 below.

Table 1. Parent-Child Variables, Measures, Informant, Items, Assessment Time-points*, Reliability, Validity

Variables	Measure(s)	Informant	# of Items	When Assessed	Reliability	Validity Evidence
Child Behavior Problems (parent)	Child Behavior Checklist (CBCL/1½-5) (Externalizing Scale & Internalizing Scale)	Parent	99	T1, T2, T3	.86-.89	[40; 41]
Child Behavior Problems (observed)	Dyadic Parent-Child Interaction Coding System (DPICS) (non-compliance, destructives, physical negatives, smart talk, cry, whine, yell)	Observer	7	T1, T2, T3	.73	[22; 57; 58]
Parent Self-Efficacy	Toddler Care Questionnaire (TCQ)	Parent	38	T1, T2, T3	>.93	[22; 57; 59; 60]
Parent Discipline	Parenting Questionnaire (PQ) (Warmth, Following Through, Corporal Punishment subscales)	Parent	50	T1, T2, T3	.68-.84	[22; 61]
Parent Depression	Center for Epidemiologic Studies Depression Scale-Revised	Parent	20	T1, T2, T3	>.85	
Parent Attachment	Attachment Style Questionnaire	Parent	40	T1	Test-retest .75-.80	
Parent Behavior	DPICS (Praise, Commands, Physical Coerciveness, Critical Statements, Positive/ Negative Affect)	Observer	10	T1, T2, T3	.88-.90	[22; 57; 58]
Social Validity: parent satisfaction w/ PT	Parent Satisfaction at end of program	Parent	4-12	T2 -CPP T3-PCIT	NA (items analyzed separately)	[34; 55; 57]
Social Validity: Degree to which parent actively participated in PT	Parent Engagement Scale	Clinician	7	T2-CPP T3-PCIT	.87	[35]

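### Objective 5 hypothesises no difference in moderation, but the plan gives no criterion that could support it, and a non-significant interaction would not

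*Combined protocol and SAP*

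**What the plan says.** Section 2, Objective 5, sets out to compare how far parent stress and depressive symptoms moderate the effect of each program. It then predicts: "It is hypothesized that there will be no difference between PCIT and CPP in the moderating effects of baseline parent stress and depressive symptoms". The prediction covers both parent and child behavior. It is a numbered objective, separate from the exploratory aim that follows it.

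Section 7c describes the testing: "Hypothesis testing will mainly be conducted using repeated-measures MANOVA", with univariate ANOVA if the MANOVA is significant, and "All baseline difference analyses and hypothesis testing will be conducted using 2-tailed tests and alpha =.05". It does not name an arm-by-moderator term. Section 4a adds only that the influence of depression and stress on outcomes will be looked at.

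Section 7c does set an equivalence null for one quantity: "the absolute difference in the post intervention means between the CPP and PCIT groups will be > 0.5 standard deviations". It equates this margin with 5 points on the CBCL. The power statement concerns the same quantity: "with 300 participants (150/condition) we will have 99% power to detect this difference using a two-sample comparison of means with alpha=0.05". No margin, confidence-interval rule or power is given for a difference in moderation.

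**The concern.** Objective 5 predicts a null result. An ordinary two-tailed test can reject a null but cannot establish it, so a non-significant interaction may mean either that moderation is alike in the two arms or that the estimate is too imprecise to tell.

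The equivalence test on CBCL means does not fill the gap. A mean difference near zero is compatible with CPP doing better than PCIT at low stress and worse at high stress. Nor does the 99% power carry over, because an interaction is estimated less precisely than a main effect.

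At stake is a statement that the two programs work alike whatever the parent's stress or depression. Section 1 makes highly stressed, impoverished families the reason for the trial, so readers would rely on that statement. Section 3 reports that stress and depression did not moderate outcomes in an earlier CPP trial. That trial compared CPP with a control group and cannot settle CPP against PCIT.

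**Working it through.** **Inputs from the documents.** 150 per arm, two-sided alpha 0.05 and a margin of 0.5 SD = 5 CBCL points, hence SD = 10 points (all Section 7c). Outcomes are measured at "three assessment phases: baseline, 4 months post-baseline, and 9 months post-baseline" (Section 4b), so baseline adjustment is possible.

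**Assumptions, not in the documents.** Normal approximation; residual SD 1; continuous moderator scaled to SD 1; baseline-outcome correlation of 0, 0.5 or 0.7; loss of 0%, 20% or 36%. The 36% borrows the PCIT treatment-dropout figure that Section 3 cites from an earlier study. It is applied here to both arms as a pessimistic case and is not a forecast of missed assessments.

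**Step 1: the plan's own figure.** SE of the mean difference = sqrt(1/150 + 1/150) = 0.1155 SD. Power for 0.5 SD = Phi(0.5/0.1155 - 1.96) = Phi(2.37) = 99%. Two one-sided tests at 0.05 each, with a true difference of 0, give 2 x Phi(4.33 - 1.645) - 1 = 99%. The stated 99% reproduces either way, but for the main effect.

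**Step 2: precision of the interaction.** SE of the difference in slopes = sqrt(1/150 + 1/150) = 0.1155 SD per SD of moderator. From -1 SD to +1 SD the CPP-PCIT difference changes by twice the slope difference, so the SE of that change = 2 x 0.1155 = 0.231 SD (equivalently 4/sqrt(300)). The 95% CI half-width is 1.96 x 0.231 = 0.45 SD, or 4.5 CBCL points. The change detectable with 80% power is 2.80 x 0.231 = 0.65 SD, or 6.5 points.

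**Step 3: chance of missing a 0.5 SD (5-point) change.** SE = 4 x sqrt(1 - r^2)/sqrt(N), where r is the baseline correlation. Power = Phi(0.5/SE - 1.96); the opposite tail is negligible.

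| Case | SE (SD) | Power | Missed |
|---|---|---|---|
| N = 300, unadjusted | 0.231 | 58% | 42% |
| N = 300, correlation 0.5 | 0.200 | 71% | 29% |
| N = 300, correlation 0.7 | 0.165 | 86% | 14% |
| N = 240 (20% loss), unadjusted | 0.258 | 49% | 51% |
| N = 192 (36% loss), unadjusted | 0.289 | 41% | 59% |

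Adjustment and loss pull in opposite directions: 20% loss with correlation 0.5 gives 61% power (39% missed). A simulation of the unadjusted N = 300 case with a continuous moderator (4,000 runs) gave 57% power. For a 1.0 SD change at N = 300, unadjusted, power is Phi(1.0/0.231 - 1.96) = 99%.

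**Step 4: what intervals at two moderator levels could show.** The SE of the CPP-PCIT difference at -1 SD or at +1 SD = sqrt(0.1155^2 + 0.1155^2) = 0.163 SD. The two estimates are uncorrelated, because the variances of the mean and slope components are equal and cancel in the covariance. A 95% CI lies inside +/-0.5 SD when the estimate is within 0.5 - 1.96 x 0.163 = 0.18 SD of zero. With truly no difference that has probability 2 x Phi(0.18/0.163) - 1 = 73% at each level, and 0.73^2 = 53% for both. With correlation 0.5 or 0.7 the joint probability is 78% or 96%.

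Clustering of CPP parents within groups and the MANOVA gate over several outcomes are not modelled. Clustering would tend to lower power.

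**The case against.** **The decision rule is inferred.** A reader might infer that the plan commits to declaring no difference whenever the interaction is non-significant. The documents do not say so. Objective 5 opens by asking about the degree of moderation, which is closer to estimation. Section 7c says only that testing is mainly by MANOVA, which leaves room for another method, and its CBCL null is framed correctly for equivalence. This stands, and it limits the point to a missing criterion. It does not remove the point, since nothing else in the plan could lead to the predicted conclusion.

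**The missed effects need not be clinically relevant.** A reader might infer that the trial would often hide an important disadvantage for stressed parents. The plan's figures do not show that. With no overall mean difference, a 0.5 SD change from -1 SD to +1 SD leaves CPP 0.25 SD (2.5 points) behind at +1 SD, inside the 0.5 SD margin. For CPP to be 0.5 SD behind there, the change must be 1.0 SD, which has 99% power on complete data. Smaller changes can take CPP beyond the margin at +1 SD only if the overall mean already favours PCIT. This stands as a limit on the consequences; it does not make non-significance evidence of equal moderation.

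**No single miss rate is robust.** Baseline adjustment would lower it and loss would raise it. This also stands, and is why a range is given.

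**The trial was sized on CBCL means, with no power claim for moderation.** True, but Objective 5 still carries a specific prediction and needs a way to judge it.

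**Conclusion.** The point holds as a missing criterion. As written, the plan has no valid route from its tests to the conclusion that Objective 5 predicts. The 42% miss rate is specific to a 0.5 SD change, complete data and no adjustment; across the other single-assumption cases examined it runs from 14% to 59%. The 0.5 SD benchmark is itself borrowed from the CBCL margin for means, because the plan sets none for moderation. The test would rarely miss a 1.0 SD change.

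Equivalence of the arms at two moderator levels must also be kept apart from equality of moderation: true differences of +0.20 SD and -0.20 SD at those levels both lie inside 0.5 SD although the slopes differ. None of this undermines the plan's equivalence comparison of CBCL means.

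**What to change.** Restate Objective 5 as estimation, and add to Section 7c:

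- For each moderator and outcome, report the arm-by-moderator interaction with its 95% CI, and the CPP-PCIT difference with its 95% CI at -1 SD and +1 SD of the moderator.
- State that a non-significant interaction will not be read as no difference.
- For CBCL, if both of those CIs lie inside the 0.5 SD margin, claim only that the programs are equivalent at those stress or depression levels, not that moderation is equal.
- For the parenting outcomes, make no such claim unless a margin is set in advance.

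No new data are needed. The costs are some wording, a few model-based estimates and, if claims on parenting outcomes are wanted, the work of justifying margins for them. The main downside is that the result may often be inconclusive: even with truly no difference, both CBCL intervals fall inside the margin only about 53% of the time unadjusted. Adjusting for the baseline score, which is already collected, would improve this.
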